11.3 Statistical Analysis Plan

Tables will be created to summarize all toxicities and side effects by dose, course, organ and severity. Rates and associated 95% confidence limits will be estimated for DLTs at the RP2D, EFS at 4 months and response. Kaplan Meier methods will be used to estimate the median and 95% confidence limits for PFS and OS. Descriptive statistics will be provided for the research participant demographics and PK parameters.

11.4 Definitions

11.4.1 Response and progression

Response and progression will be evaluated every 2 cycles in this study using RECIST Version 1.1. Changes in only the largest diameter (one-dimensional measurement) of the tumor lesions are used in the RECIST Version 1.1 criteria. Note: Lesions are either measurable or non-measurable using the criteria provided below. The term “evaluable” in reference to measurability will not be used because it does not provide additional meaning or accuracy.

Measurable Disease: Measurable lesions are defined as those that can be accurately measured in at least one dimension (longest diameter to be recorded) as ≥ 20 mm with conventional techniques (CT, MRI, x-ray) or as ≥ 10 mm with spiral CT scan. All tumor measurements must be recorded in millimeters (or decimal fractions of centimeters).

Non-Measurable Disease: All other lesions (or sites of disease), including small lesions (longest diameter <20 mm with conventional techniques or <10 mm using spiral CT scan), are considered non-measurable disease. Bone lesions, leptomeningeal disease, ascites, pleural/pericardial effusions, lymphangitis cutis/pulmonis, inflammatory breast disease, abdominal masses (not followed by CT or MRI), and cystic lesions are all non-measurable.

Target Lesions: All measurable lesions up to a maximum of five lesions per organ and 10 lesions in total, representative of all involved organs, should be identified as **target lesions** and recorded and measured at baseline. Target lesions should be selected on the basis of their size (lesions with the longest diameter) and their suitability for accurate repeated measurements (either by imaging techniques or clinically). A sum of the longest diameter (LD) for all target lesions will be calculated and reported as the baseline sum LD. The baseline sum LD will be used as reference by which to characterize the objective tumor response.

Non-Target Lesions: All other lesions (or sites of disease) should be identified as **non-target lesions** and should also be recorded at baseline. Non-target lesions include measurable lesions that exceed the maximum numbers per organ or total of all involved organs as well as non-measurable lesions. Measurements of these lesions are not required but the presence or absence of each should be noted throughout follow-up.

11.4.2 Guidelines for evaluation of measurable disease

All measurements should be taken and recorded in metric notation using a ruler or calipers. All baseline evaluations should be performed as closely as possible to the beginning of treatment and never more than 4 weeks before the beginning of the treatment.

Note: Tumor lesions that are situated in a previously irradiated area might or might not be considered measurable. If the investigator thinks it appropriate to include them, the

conditions under which such lesions should be considered must be defined in the protocol.

The same method of assessment and the same technique should be used to characterize each identified and reported lesion at baseline and during follow-up. Imaging-based evaluation is preferred to evaluation by clinical examination when both methods have been used to assess the antitumor effect of a treatment.

Clinical Lesions: Clinical lesions will only be considered measurable when they are superficial (e.g., skin nodules and palpable lymph nodes). In the case of skin lesions, documentation by color photography, including a ruler to estimate the size of the lesion, is recommended.

Chest X-Ray: Lesions on chest x-ray are acceptable as measurable lesions when they are clearly defined and surrounded by aerated lung. However, CT is preferable.

Conventional CT and MRI: These techniques should be performed with cuts of $\leq 10\text{mm}$ in slice thickness contiguously. Spiral CT should be performed using a 5mm contiguous reconstruction algorithm. This applies to tumors of the chest, abdomen, and pelvis. Head and neck tumors and those of extremities usually require specific protocols.

Ultrasound: When the primary endpoint of the study is objective response evaluation, ultrasound should not be used to measure tumor lesions. It is, however, a possible alternative to clinical measurements of superficial palpable lymph nodes, subcutaneous lesions, and thyroid nodules. Ultrasound might also be useful to confirm the complete disappearance of superficial lesions usually assessed by clinical examination.

Endoscopy and Laparoscopy: The utilization of these techniques for objective tumor evaluation has not yet been fully and widely validated. Their uses in this specific context require sophisticated equipment and a high level of expertise that may only be available in some centers. Therefore, the utilization of such techniques for objective tumor response should be restricted to validation purposes in reference centers. However, such techniques can be useful to confirm complete pathological response when biopsies are obtained.

Tumor Markers: Tumor markers alone cannot be used to assess response. If markers are initially above the upper normal limit, they must normalize for a patient to be considered in complete clinical response. Specific additional criteria for standardized usage of CA-125 response in support of clinical trials are being developed.

Cytology and Histology: These techniques can be used to differentiate between partial responses (PR) and complete responses (CR) in rare cases (e.g., residual lesions in tumor types, such as germ cell tumors, where known residual benign tumors can remain).

The cytological confirmation of the neoplastic origin of any effusion that appears or worsens during treatment when the measurable tumor has met criteria for response or

stable disease is mandatory to differentiate between response or stable disease (an effusion may be a side effect of the treatment) and progressive disease.

11.4.3 Response criteria

11.4.3.1 Evaluation of target lesions

CR: Disappearance of all target lesions.

PR: At least a 30% decrease in the sum of the longest diameter (LD) of target lesions, taking as reference the baseline sum LD.

Progressive Disease (PD): At least a 20% increase in the sum of the LD of target lesions, taking as reference the smallest sum LD recorded since the treatment started or the appearance of one or more new lesions.

Stable Disease (SD): Neither sufficient shrinkage to qualify for PR nor sufficient increase to qualify for PD, taking as reference the smallest sum LD since the treatment started.

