11.4.3.3 Evaluation of best overall response

The best overall response is the best response recorded from the start of the treatment until disease progression/recurrence (taking as reference for progressive disease the smallest measurements recorded since the treatment started). The patient's best response assignment will depend on the achievement of both measurement and confirmation criteria.

Target Lesions	Non-Target Lesions	New Lesions	Overall Response
CR	CR	No	CR
CR	Incomplete response/SD	No	PR
PR	Non-PD	No	PR

SD	Non-PD	No	SD
PD	Any	Yes or No	PD
Any	PD	Yes or No	PD
Any	Any	Yes	PD

Note: Patients with a global deterioration of health status requiring discontinuation of treatment without objective evidence of disease progression at that time should be classified as having “symptomatic deterioration.” Every effort should be made to document the objective progression, even after discontinuation of treatment.

In some circumstances, it may be difficult to distinguish residual disease from normal tissue. When the evaluation of complete response depends on this determination, it is recommended that the residual lesion be investigated (fine needle aspirate/biopsy) before confirming the complete response status.

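### The target-lesion progression rule in 11.4.3.1 has no minimum absolute increase and, read literally, leaves the baseline scan out of its reference, so 4-month EFS can be misclassified in both directions

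*Combined protocol and SAP*

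**What the plan says.** - Section 11.4.1 names the standard: "Response and progression will be evaluated every 2 cycles in this study using RECIST Version 1.1". Section 4.2 and the synopsis name it too. Section 11.4 then prints its own criteria and does not say which prevails if the two differ.
- Section 11.4.3.1 sets the progression threshold at "At least a 20% increase in the sum of the LD of target lesions". No minimum rise in millimetres appears anywhere in 11.4. The comparator for that threshold, given together with the new-lesion route, reads: "smallest sum LD recorded since the treatment started or the appearance of one or more new lesions". The partial-response line in the same section names the baseline sum as its reference; the progression line does not.
- Section 11.4.3.3 repeats the reference: "taking as reference for progressive disease the smallest measurements recorded since the treatment started". Section 11.4.3.4 does so as well.
- Section 11.4.2 puts the baseline scan before treatment, "never more than 4 weeks before the beginning of the treatment", and says of image quality: "Spiral CT should be performed using a 5mm contiguous reconstruction algorithm".
- Section 11.4.1 makes a lesion of 10 mm measurable on spiral CT.
- Section 11.1.2 bases both Simon stages on the number of patients event free at 4 months: at least 6 of 12 to continue, at least 16 of 27 for success, with rates of 45% and 70% and both errors at 0.1. No section defines an EFS event.

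**The concern.** Two faults follow from the printed rule.

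(a) A purely relative threshold applied to a small sum is crossed by a change smaller than the image reconstruction interval. Because the reference is the smallest sum, patients whose tumours have shrunk are the most exposed.

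(b) If only sums recorded after treatment began count, the first on-study scan is its own reference. Target-lesion growth from baseline to that scan then cannot be progression.

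Progression is the natural main component of EFS, and EFS decides whether accrual continues and whether the combination is taken further. Fault (a) would turn true non-events into failures; fault (b) would let some true failures count as successes.

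**Working it through.** **1. The plan's design.** With X1 ~ Bin(12, p) and X2 ~ Bin(15, p), P(success) = Σ over x = 6 to 12 of P(X1 = x) · P(X2 ≥ 16 − x). This gives 0.091 at p = 0.45 and 0.903 at p = 0.70. The stated 0.1 limits are met, with almost no slack on power.

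**2. Fault (a), arithmetic.** Rise needed = 0.20 × smallest sum.

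| Smallest sum (mm) | Rise that is progression (mm) |
|---|---|
| 5 | 1.0 |
| 7 (a 10 mm lesion after a 30% decrease) | 1.4 |
| 10 | 2.0 |
| 15 | 3.0 |
| 20 | 4.0 |
| 50 | 10.0 |

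A lesion reading 12, then 5, then 6 mm has halved from baseline, yet is progressive at the third reading on 1 mm. A 5 mm minimum would bind for sums below 5 / 0.20 = 25 mm.

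**3. Fault (b), arithmetic.** Scans fall every 2 × 21 = 42 days, so days 42 and 84 precede 4 months (about day 122), and day 126 follows it.
- 50 → 75 → 80 mm: at week 6 the only sum since treatment began is 75. At week 12, 80/75 = 1.067, below 1.20. It is never target-lesion progression. With baseline included, 75/50 = 1.50 is progression at week 6.
- 50 → 75 → 90 mm: 90/75 = 1.20, so it is progression at week 12, still before 4 months.

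**4. False progression from reading error.** The documents give no reading error, so a standard deviation of 1.0 to 1.5 mm for the sum is assumed. Simulation: 400,000 truly unchanged single lesions, read at baseline, week 6 and week 12, normal error, rounded to 1 mm.

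| 10 mm lesion, false progression by week 12 | 1.0 mm | 1.5 mm |
|---|---|---|
| Literal rule (week 12 against week 6 only) | 15% | 23% |
| Baseline included, baseline reading at least 10 mm | about 20% | about 31% |
| Baseline included, 5 mm minimum added | 0.3% | 5% |

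The second row requires a baseline reading of at least 10 mm because a smaller lesion is not measurable under 11.4.1. The third row does not impose that condition. Without rounding, the literal figures are 10% and 20%. At a sum of 30 mm the rate is 1.5% or less over the same error range.

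**5. Effect on power.** Let q be the share of patients with such disease (assumed 20%; the documents give no tumour burden) and f the false-progression rate. The observed rate is 0.70 × (1 − q f).
- f = 0.15: 0.679, power 0.856
- f = 0.20: 0.672, power 0.838
- f = 0.23: 0.668, power 0.827
- f = 0.31: 0.657, power 0.794

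**6. Effect on type I error.** If a fraction m of true events is missed, the observed rate at p = 0.45 is 0.45 + 0.55 m.
- m = 0.02: 0.461, type I error 0.111
- m = 0.05: 0.4775, type I error 0.147
- m = 0.10: 0.505, type I error 0.222

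These values of m are illustrative; the documents do not allow m to be estimated.

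**The case against.** The best defence is that RECIST 1.1 is named as the standard, so an assessor may apply that standard instead of the printed summary. Section 11.4.1 also makes the baseline sum the reference for objective response, and leaving baseline out makes target-lesion progression impossible at the first scan, which can hardly be intended. This is fair on intent. It does not settle the wording: 11.4 prints a full set of operative criteria with no precedence statement, and an assessor who follows it is following the protocol. The independent review in 11.4.3.5 covers responses at study completion. It does not say that it covers progression, and it comes after the stage 1 decision.

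Several limits on the point do stand:
- New lesions and unequivocal non-target progression count at any scan, and a further 20% rise by week 12 is caught. Only target-only growth that then slows escapes, so one should not infer that early progressors in general would be counted event free.
- The target-lesion rule does not touch patients with only non-measurable disease, whom 5.1 admits.
- Simulating with baseline included and no condition on the baseline reading gives 33 to 48% false progression, and a 40% rate with a 20% share would put power near 0.75. Those figures do not describe this rule: they include baseline, which the literal wording leaves out, and they admit baseline readings below 10 mm, which 11.4.1 makes non-measurable.
- A reader might infer that different sites would score the same scans differently. Section 14.7 makes this a single-centre study.
- A reader might also take the target-lesion count, "All measurable lesions up to a maximum of five lesions per organ and 10 lesions in total", or the use of longest diameter for every lesion as departures from RECIST 1.1. The documents do not reproduce that standard, so they cannot show this.

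**Conclusion.** The point holds as a defect in a written endpoint rule. Followed as printed, 11.4.3.1 calls progression on 1 to 3 mm when the smallest sum is 5 to 15 mm, and does not call target-only growth at the first scan. Naming RECIST 1.1 without saying that it prevails does not cure this.

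The effect on EFS is conditional on progression being an EFS event, which is likely but unstated. The two biases oppose each other and their net size is unknown. For fault (a) alone, power falls from 0.903 to about 0.83 to 0.86 on the literal reading, or about 0.79 to 0.84 with baseline included. Both ranges rest on three assumptions: a reading error of 1.0 to 1.5 mm, 1 mm rounding, and 20% of patients with a single lesion near 10 mm. For sums of 30 mm and above the effect is negligible under the same error assumption.

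The faults are linked. Under the literal wording, reading error can act only at week 12; adding baseline to the reference without a minimum rise lets it act at week 6 as well, so false progressions increase.

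**What to change.** 1. In 11.4.3.1, 11.4.3.3 and 11.4.3.4, define the progression reference as the smallest sum on study, including the baseline sum.
2. In the same amendment, require a minimum absolute increase in addition to 20%. A 5 mm minimum is one example, matching the reconstruction interval in 11.4.2. Alternatively, state that the named RECIST 1.1 criteria prevail over the printed text. Do not make change 1 alone.
3. State in 11.1.2 or 11.4 that progression so defined is an EFS event.
4. Re-score the recorded measurements of patients treated at any candidate RP2D, since the 12 at the chosen dose form stage 1.

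The cost is protocol wording and a re-score of existing measurements, with no new scans. The small downside is that a few true progressions in very small lesions would be called one scan later.

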11.4.3.2 Evaluation of non-target lesions

Complete Response (CR): Disappearance of all non-target lesions and normalization of tumor marker level.

Incomplete Response/ Stable Disease (SD): Persistence of one or more non-target lesion(s) and/or maintenance of tumor marker level above the normal limits.

Progressive Disease (PD): Appearance of one or more new lesions and/or unequivocal progression of existing non-target lesions.

Although a clear progression of “non-target” lesions only is exceptional, in such circumstances the opinion of the treating physician should prevail, and the progression status should be confirmed at a later time.

Note: If tumor markers are initially above the upper normal limit, they must normalize for a patient to be considered in complete clinical response.

11.4.3.3 Evaluation of best overall response

The best overall response is the best response recorded from the start of the treatment until disease progression/recurrence (taking as reference for progressive disease the smallest measurements recorded since the treatment started). The patient's best response assignment will depend on the achievement of both measurement and confirmation criteria.

Target Lesions	Non-Target Lesions	New Lesions	Overall Response
CR	CR	No	CR
CR	Incomplete response/SD	No	PR
PR	Non-PD	No	PR

SD	Non-PD	No	SD
PD	Any	Yes or No	PD
Any	PD	Yes or No	PD
Any	Any	Yes	PD

Note: Patients with a global deterioration of health status requiring discontinuation of treatment without objective evidence of disease progression at that time should be classified as having “symptomatic deterioration.” Every effort should be made to document the objective progression, even after discontinuation of treatment.

In some circumstances, it may be difficult to distinguish residual disease from normal tissue. When the evaluation of complete response depends on this determination, it is recommended that the residual lesion be investigated (fine needle aspirate/biopsy) before confirming the complete response status.

11.4.3.4 Confirmatory measurement/duration of response

Confirmation: To be assigned a status of PR or CR, changes in tumor measurements must be confirmed by repeat assessments that should be performed no less than 4 weeks after the criteria for response are first met. In the case of SD, follow-up measurements must have met the SD criteria at least once after study entry at a minimum interval of 8 weeks.

Duration of Overall Response: The duration of overall response is measured from the time measurement criteria are met for CR or PR (whichever is first recorded) until the first date that recurrent or progressive disease is objectively documented (taking as reference for progressive disease the smallest measurements recorded since the treatment started).

The duration of overall CR is measured from the time measurement criteria are first met for CR until the first date that recurrent disease is objectively documented.

Duration of Stable Disease: Stable disease is measured from the start of the treatment until the criteria for progression are met, taking as reference the smallest measurements recorded since the treatment started.

11.4.3.5 Response review

All responses will be reviewed by an expert(s) independent of the study at the study's completion. This will include simultaneous review of the patients' files and radiological images.

12.0 Correlative Translational Studies

12.1 Pharmacokinetics

Patients enrolled in the expanded cohort at the MTD will be asked to undergo serial blood sampling to evaluate the PK of everolimus and eribulin. Although it is unlikely that

these two agents will interact negatively, both drugs are substrates for the membrane transporter P-glycoprotein. Therefore, PK studies will be performed in the expanded cohort treated at the MTD to evaluate the PK of the drug combination.³²⁻³⁴

All PK/Plasma Samples will be sent to:

[name]
Analytical Pharmacology Core Facility (APCF)
[name]
Beckman Research Institute/City of Hope
[name]
[contact]
Fax – [contact]
Email – [contact]

12.1.1 Everolimus PK sampling (whole blood)

At each of the time points below (**Section 12.3.1**), 5ml of anti-coagulated whole blood will be collected into a purple-top Vacutainer® tube containing EDTA for determination of everolimus. These tubes should be inverted several times to mix. Blood samples should be kept on ice until they can be transferred to the freezer. If you are using plastic Vacutainer ® tubes, the samples can be directly frozen at <-20°C. If glass tubes are used for collection, whole blood must be transferred to polypropylene vials prior to being frozen at <-20°C. **In either case, plasma should not be separated from whole blood.**

12.1.2 Eribulin PK sampling (plasma)

At each of the time points below (**Section 12.3.1**), 5mL of anti-coagulated whole blood will be collected in green-top Vacutainer ® tubes (sodium or lithium heparin) from a site distal to the site of drug administration at the times shown in the table below. Blood samples will be kept on ice until plasma is separated from whole blood by centrifugation at 1500 x g (within 1 hour). Plasma will be transferred to appropriately labeled polypropylene tubes and stored at <-70°C until analysis. A separate PK flow sheet will be used to record the actual times of blood draws, urine collections and other pertinent information. Each sample will be labeled with the patient's name, medical record number, date of collection, scheduled sample collection time and actual sample collection time.

12.1.3 Sampling Schedule

Everolimus Sample Collection

PK Time Point	Sample Type	Cycle	Day	Collection time 24-hour clock)
WB1	Whole Blood	1	D1 +/- 10 min	00:00
WB2	Whole Blood	1	D1 +/- 10 min	01:00
WB3	Whole Blood	1	D1 +/- 10 min	02:00

WB4	Whole Blood	1	D1 +/- 10 min	04:00
WB5	Whole Blood	1	D1 +/- 10 min	06:00
WB6	Whole Blood	1	D2 +/- 2 hours	24:00
WB7	Whole Blood	2	D1 +/- 10 min	00:00
WB8	Whole Blood	2	D1 +/- 10 min	01:00
WB9	Whole Blood	2	D1 +/- 10 min	02:00
WB10	Whole Blood	2	D1 +/- 10 min	04:00
WB11	Whole Blood	2	D1 +/- 10 min	06:00
WB10	Whole Blood	2	D2 +/- 2 hours	24:00

Eribulin Sample Collection

PK Time Point	Sample Type	Cycle	Day	Sample Description	Collection time 24-hour clock)
P1	Plasma	2	D1	Pre	00:00
P2	Plasma	2	D1	End of infusion	00:05
P3	Plasma	2	D1	10 min	00:10
P4	Plasma	2	D1	15 min	00:15
P5	Plasma	2	D1	30 min	00:30
P6	Plasma	2	D1	1 hr +/- 10 min	01:00
P7	Plasma	2	D1	2 hr +/- 10 min	02:00
P8	Plasma	2	D1	4 hr +/- 10 min	04:00
P9	Plasma	2	D1	6 hr +/- 10 min	06:00
P10	Plasma	2	D2	24 hr +/- 2 hours	24:00
P11	Plasma	2	D3	48 hr +/- 3 hours	48:00
P12	Plasma	2	D4	72 hr +/- 3 hours	72:00
P13	Plasma	2	D8	167 hr +/- 3 hours	167:00

12.1.4 Analytical methods

12.1.4.1 Everolimus blood concentrations

Everolimus blood concentrations will be determined in all samples in the Analytical Pharmacology Core Facility (APCF) at the City of Hope using a validated LC-MS/MS method. Briefly, following sample clean-up and LC separation from interfering substances in whole blood, a Micromass Quattro Ultima triple quadrupole mass spectrometer operating in positive ion mode is used to detect everolimus according to the mass transition of m/z 975.5 → 908.5 with tacrolimus (m/z 821.5 → 768.5) as the internal standard. The limit of quantitation for everolimus in whole blood is 0.25ng/ml.

